Study Protocol Cover Page

Study Title: Mindfulness-Based Stress Reduction to Improve Neuropsychological Functioning in Acquired Brain Injury

Clinical Trials ID: NCT03969563

Document date/IRB approval date: 10/31/2019

Treatment Protocol

We conducted six rounds of each class (see Table 2 for course topics and descriptions). To reduce variability, both courses had the same instructor - a trained and certified MBSR instructor with over 10 years of experience and a Master's degree in Education (emphasis on Curriculum and Instruction) - making her well-qualified to teach both classes. The instructor also received specialized training for teaching MBSR and other educational courses online. Both classes were further matched in terms of the length (2.5 hours/week), schedule (9-week class plus a day-long retreat), class size (7-10 participants), instructor, and amount of homework. All participants were also informed at the beginning of the course that their data would be excluded from the study if they missed more than three classes.

The MBSR class was the standardized program created by the University of Massachusetts, which includes an introductory session, 8 weeks of classes, and a retreat during the sixth week (Kabat-Zinn, 1990b). During the course, participants learned about mindfulness through practices such as body awareness, mindful movement, meditation, and informal mindfulness practices of daily life (e.g., eating, communicating, working, coping). The retreat included a review of class material, meditation and yoga practice, and a group lunch. Our study modified this program slightly by reducing the retreat day to four hours. And, given the population and the course modality, participants completed smaller movement and chair yoga exercises instead of the standard yoga practices. For homework, MBSR participants were assigned practices according to the standard MBSR curriculum, where they followed along to different meditation recordings (provided to them through a web link), engaged in mindful movement, and read from the course manual. The time spent engaging in mindfulness practices were then tracked using online homework logs.

Our active intervention, the Brain Health class, was a modification of an existing VA education class for brain-injured individuals taught on the VA campus. It served as a robust active control because it matched the MBSR intervention in terms of instructor, time interacting with peers and the instructor, movement, schedule, and homework activities. The Brain Health class did not include any meditative/ mindfulness components, which we hypothesized would be the critical factor for how MBSR leads to improved health and cognition (Kabat-Zinn, 1990b).

Specifically, each class consisted of lectures with slides and videos (90 mins) and a group discussion (45 mins), during which time participants learned basic brain anatomy, how brain injuries can affect their cognition, and completed classes on the importance of topics such as sleep, nutrition, and social connection. To match the movement portion of the MBSR class, the Brain Health class also included simple chair exercises, such as stretching and reaching. The Brain Health retreat consisted of a review of class topics, short videos on brain topics, and a group lunch.

Measures

Study Implementation and Satisfaction. We measured study feasibility by examining rates of recruitment (i.e., the percentage of participants who agreed to take part in the study, relative to the total number of people we contacted) and retention (i.e., how many participants completed the program, attendance, homework engagement, and instructor-rated class engagement). Participants were also asked to complete an anonymous nine-item questionnaire created by the authors (see Table 3) to assess course satisfaction. Participants thus used a scale of 1 (very unsatisfied) to 5 (very satisfied) to answer questions such as, "How satisfied were you with the class?" and "How likely are you to continue to study and practice the skills you learned in this class?".

Mood, Well-Being, and Health. The Geriatric Depression Scale (Yesavage et al., 1982) was administered to measure subjective symptoms of depression in an older adult population. Participants indicated yes (1) or no (0) to questions such as, "*Do you feel happy most of the time?*" and "*Do you feel your situation is hopeless?*". The State-Trait Anxiety Inventory (Spielberger et al., 1983) measured current anxiety symptoms. Participants used a 1 (almost never) to 4 (almost always) scale to express how often they "feel content," and "feel calm."

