## **Data Analytic Approach**

Preliminary analyses examined potential class differences (i.e., MBSR, Brain Health) in participant demographics (i.e., sex, age, education). Variables that differed across groups were included as covariates when appropriate. For primary analyses, we examined measures collected at one timepoint (i.e., implementation, satisfaction), using a multivariate ANOVA (MANOVA) as an omnibus test for measures with multiple dependent variables. If post-hoc analyses were completed, Bonferroni adjusted pvalues were applied. Pairwise comparisons were examined with independent t-tests for continuous variables and Chi-square analyses for binary variables. For outcome variables collected at multiple timepoints (i.e., cognitive functioning, health and wellbeing measures), linear mixed effects models ("Ime4" package v. 1.1–21 in "R" v. 3.6.3) were used to examine each outcome. Class (MBSR, Brain Health) and time (preintervention, post-intervention, and six month follow-up) were entered as fixed effects, participants were entered as a random effect, and the outcome variable was entered as a dependent variable. Main effects of class and time, as well as the class x time interaction (reflecting intervention effects) were examined.

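### Excluding anyone who misses more than three classes turns the class-by-time test into a comparison of people selected on attendance after the course began, and no all-enrolled analysis is given in the text available

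*Protocol*

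**What the plan says.** The Treatment Protocol section reports the rule as something announced to everyone in both classes when the course started: "their data would be excluded from the study if they missed more than three classes". It does not say how the rule was applied, which data it covers, or whether the retreat counts as a class.

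On scale, the same section says "We conducted six rounds of each class", with 7 to 10 people per class and nine weeks of classes plus a retreat. It says the MBSR programme "includes an introductory session, 8 weeks of classes, and a retreat during the sixth week". The introductory session plus eight weeks makes the stated nine, so only the status of the retreat is open.

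The Measures section (Study Implementation and Satisfaction) counts attendance and programme completion among its retention measures.

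The SAP's Data Analytic Approach fits a linear mixed model to each repeated outcome, in which "participants were entered as a random effect", and states that main effects and the "class x time interaction (reflecting intervention effects) were examined". It names no analysis population, no all-enrolled or sensitivity analysis, and no comparison of excluded with retained participants. One part of the SAP was not available for this review, so statements about what is absent apply only to the text supplied.

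**The concern.** Attendance is observed after the course begins and can be affected by the course itself. The classes are matched on instructor, schedule, class size and homework, but by design they differ in content. Matching therefore does not guarantee that the same number, or the same kind, of people miss four or more sessions. The study itself treats attendance as an outcome, so the rule conditions the efficacy comparison on an outcome.

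A stable difference in level between attenders and non-attenders cancels in the interaction. A difference in change does not, unless it removes the same amount from both classes. The planned covariates are sex, age and education where these differ between groups, and they do not address this. A mixed model can use partial data from people with missed visits, but not from people whose data are removed.

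A second point is conditional. If the exclusion also covers the implementation data, reported attendance has a floor set by the rule, and completion is affected in the same way. If feasibility is counted on everyone enrolled, this point does not arise.

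**Working it through.** The text supplied gives no sample size, exclusion rate, SD or effect size, so there is no stated figure to reproduce. Everything below except the class counts is assumed.

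**Inputs from the protocol.** Six rounds of each class with 7 to 10 people give 6 × 7 = 42 to 6 × 10 = 60 per class, or 84 to 120 in all. This total is derived, not stated, and the text does not say whether class size is before or after exclusions.

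**Bias in the interaction, no true effect.** Let p be the share excluded in a class and d the gap in mean change between attenders and those excluded, in outcome SD units. If the whole class has mean change 0, attenders have mean change p·d. The bias is p₁d₁ − p₀d₀.

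The SD of change is √(2(1 − r)), which is 0.775 at r = 0.7. The standard error uses (N/2)(1 − p) people per class, and the test is a two-sided 5% normal test on one pre-post change.

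Example: 20% v 10%, d = 0.5, N = 84.
- Bias: 0.20 × 0.5 − 0.10 × 0.5 = 0.05.
- People retained: 42 × 0.8 = 33.6 and 42 × 0.9 = 37.8.
- Standard error: 0.775 × √(1/33.6 + 1/37.8) = 0.184.
- Ratio: 0.05/0.184 = 0.27, which gives a rejection rate of 5.9%.

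| Excluded | d | Bias (SD) | Type I error, N 84-120, r = 0.7 |
|---|---|---|---|
| equal shares, equal d | any | 0 | 5.0% |
| 15% v 10% | 0.5 | 0.025 | 5.2-5.3% |
| 20% v 10% | 0.3 | 0.03 | 5.3-5.4% |
| 20% v 10% | 0.5 | 0.05 | 5.9-6.2% |
| 30% v 10% | 0.5 | 0.10 | 8.2-9.6% |

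With r from 0.5 to 0.8, the 15% v 10% row becomes 5.1-5.5% and the 30% v 10% row 6.9-12.0%.

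**Equal shares are not enough.** Suppose 20% are excluded from each class by truncating an attendance score that has correlation ρ with change. Attenders' mean change is then ρ × 0.280/0.8, in units of the SD of change. If ρ has opposite signs in the two classes, the bias is twice that: 0.14 at ρ = 0.2 and 0.35 at ρ = 0.5.

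**Attendance, only if the exclusion covers it.** A retained person attended at least 6/9 = 66.7% of sessions, or 7/10 = 70% if the retreat counts. The overstatement is the mean attendance of those with at least n − 3 sessions, minus the true mean. Each range runs from independent absences (binomial) to strongly clustered absences (beta-binomial, within-person correlation 0.20).

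| True mean | Excluded, 9 sessions | Overstatement, 9 sessions (points) | Overstatement, 10 sessions (points) |
|---|---|---|---|
| 75% | 16.6-25.5% | 4.7-11.4 | 5.7-12.5 |
| 85% | 3.4-12.4% | 1.1-5.8 | 1.4-6.4 |
| 90% | 0.8-7.1% | 0.3-3.5 | 0.4-3.9 |
| 95% | 0.1-3.0% | about 0-1.5 | about 0-1.7 |

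**The case against.** **Incomplete text.** Part of the SAP was unavailable, and a population definition could sit there. The protocol reports what participants were told, and the SAP neither repeats the rule nor restricts its model by attendance, so the announcement may only have been meant to encourage attendance. This stands as a limit, and it is why the point is put as the rule applied as written. It does not remove the problem: the only statement available on whose data count is an exclusion based on attendance.

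**Small effect.** Three of the four unequal-loss rows leave type I error between 5.2% and 6.2%. The 30% v 10% row is extreme: even at 75% mean attendance with strong clustering, the attendance model excludes 25.5% (29.4% with 10 sessions). This is fair. Moderate imbalance does little harm, and nothing in the documents shows unequal loss.

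**Not the planned test.** With three timepoints, taken as categorical, the interaction has two degrees of freedom. With the same bias at both follow-ups and compound symmetry, at r = 0.7, type I error is about 5.8-6.1% (20% v 10%, d 0.5) and 7.9-9.2% (30% v 10%, d 0.5). This is correct but changes little.

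**Attendance figures.** Counting completers is hard to square with deleting non-completers, so feasibility was more naturally counted on everyone enrolled. This is why the point is kept conditional.

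**A legitimate estimand.** The limit was announced in advance to both classes, and a comparison of attenders can be a proper target if labelled as such. That supports keeping it as a labelled secondary result. It does not support reading it as the intervention effect among those who entered the classes.

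**Conclusion.** The concern holds. Followed as written, the rule selects the compared groups on attendance after the course began, and the text available offers no analysis of everyone enrolled.

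The direction of bias is unknown and its size may be zero. Under the assumed inputs it is small for modest imbalance and reaches 0.10 SD only at 30% v 10%. Equal counts of exclusions would not by themselves rule it out, because the kinds of people lost may differ.

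Overstatement of attendance depends on the exclusion reaching the implementation data. If it does, it occurs whenever anyone is excluded, even with equal loss in both classes. The supplied text does not describe how participants were allocated, so no claim is made about randomisation.

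**What to change.** - Make the main analysis all enrolled participants, in the class they entered or were allocated to, using every available assessment in the existing mixed model. This is valid under missing at random.
- Keep the attender-only analysis as a labelled per-protocol sensitivity analysis.
- Compute attendance, homework, engagement and completion on everyone enrolled.
- State whether the retreat counts toward the limit, and report the number exceeding it by class.

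The cost is wording in both documents and one re-run of the existing model. Reported attendance may look less favourable.

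The gain depends on follow-up already held for low attenders, because the text is retrospective. Let f be the share of them with follow-up. For a gap in change not explained by baseline, the residual mean per class is p(1 − p)d(1 − f)/(1 − p + pf), differenced between classes. For 20% v 10%, d = 0.5 and f = 0.5, this is 0.04/0.90 − 0.0225/0.95 = 0.044 − 0.024 = 0.021.

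| Case (d = 0.5) | f = 0 | f = 0.5 | f = 1 |
|---|---|---|---|
| 20% v 10% | 0.05 | 0.021 | 0 |
| 30% v 10% | 0.10 | 0.038 | 0 |

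If no follow-up exists for low attenders, the result leans on missing at random and may barely move. The population statement and the counts by class are still worth having.

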## **Data Analytic Approach**

Preliminary analyses examined potential class differences (i.e., MBSR, Brain Health) in participant demographics (i.e., sex, age, education). Variables that differed across groups were included as covariates when appropriate. For primary analyses, we examined measures collected at one timepoint (i.e., implementation, satisfaction), using a multivariate ANOVA (MANOVA) as an omnibus test for measures with multiple dependent variables. If post-hoc analyses were completed, Bonferroni adjusted pvalues were applied. Pairwise comparisons were examined with independent t-tests for continuous variables and Chi-square analyses for binary variables. For outcome variables collected at multiple timepoints (i.e., cognitive functioning, health and wellbeing measures), linear mixed effects models ("Ime4" package v. 1.1–21 in "R" v. 3.6.3) were used to examine each outcome. Class (MBSR, Brain Health) and time (preintervention, post-intervention, and six month follow-up) were entered as fixed effects, participants were entered as a random effect, and the outcome variable was entered as a dependent variable. Main effects of class and time, as well as the class x time interaction (reflecting intervention effects) were examined.

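### Holm should replace Bonferroni for post-hoc tests, and a mean satisfaction score with its confidence interval should be reported alongside the item-level MANOVA

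*SAP*

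**What the plan says.** The SAP's Data Analytic Approach puts implementation and satisfaction, each collected once, among the primary analyses. It describes "using a multivariate ANOVA (MANOVA) as an omnibus test for measures with multiple dependent variables". It then says: "If post-hoc analyses were completed, Bonferroni adjusted pvalues were applied". Pairwise comparisons use independent t-tests or chi-square tests.

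The protocol, under Measures (Study Implementation and Satisfaction), describes the satisfaction instrument as "an anonymous nine-item questionnaire created by the authors", scored from 1 to 5. Neither document defines a total or mean satisfaction score. Neither gives a sample size, effect size or significance level for this comparison. The SAP does not state that the nine items were the dependent variables. That is the natural reading of the two documents together, but it is an inference.

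**The concern.** Two features of this analysis can be improved at almost no cost.

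First, Bonferroni applies its strictest threshold to every test in a set. Holm gives the same protection against any false positive and relaxes the threshold after each rejection. Staying with Bonferroni means that some real item differences go unflagged for no return.

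Second, a nine-variable MANOVA asks whether any combination of items differs between the classes. If one class is simply more satisfied across the board, that question spreads over nine degrees of freedom a signal that one score could carry on one. The omnibus result also comes without a single effect estimate or interval, so the report would not say by how much satisfaction differed overall.

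**Working it through.** **Inputs from the documents.** There are two classes (SAP) and nine items (protocol, Measures). The protocol (Treatment Protocol) gives six rounds of each class with 7 to 10 participants, so 6 x 7 = 42 to 6 x 10 = 60 per class. These are upper figures: people who missed more than three classes were excluded, and the number excluded is not given.

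**Assumptions.** Two-sided alpha 0.05; the same shift d (in SD units) on every item; equal inter-item correlation r, taken as 0.5 with a range of 0.3 to 0.7; independent participants. The plan states no power figure, so there is none to reproduce.

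**Holm against Bonferroni.** With nine tests, Bonferroni compares every p-value with 0.05/9 = 0.0056. Holm compares the smallest with 0.05/9, the next with 0.05/8 = 0.00625, and so on up to 0.05. The first step is identical, so the chance of at least one rejection is identical. Every later threshold is larger, so Holm rejects whatever Bonferroni rejects and sometimes more. Simulated mean number of items flagged, d = 0.5, r = 0.5 (20,000 runs, normal reference):

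| Per class | Bonferroni | Holm |
|---|---|---|
| 42 | 2.8 | 3.5 |
| 60 | 4.4 | 5.3 |

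A smaller simulation with t-tests (1,500 runs) gives 2.6 against 3.3 and 4.1 against 5.1. At least one item is flagged in 74% of runs at 42 per class and 88% at 60, under either method.

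**MANOVA against a mean score, uniform shift.** With two classes the MANOVA is Hotelling's T-squared, tested on F(9, 2n - 10). Its noncentrality is (n/2) x D2, where D2 = 9d^2/(1 + 8r). The mean of nine items has variance (1 + 8r)/9, so its squared standardised difference is the same D2, but it is tested on F(1, 2n - 2).

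For d = 0.5 and r = 0.5, D2 = 9 x 0.25/5 = 0.45.
- n = 42: noncentrality 21 x 0.45 = 9.45. F(9, 74) gives 48% power; F(1, 82) gives 86%.
- n = 60: noncentrality 30 x 0.45 = 13.5. F(9, 110) gives 68%; F(1, 118) gives 95%.

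Power at r = 0.5, MANOVA v mean score:

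| d | 42 per class | 60 per class |
|---|---|---|
| 0.3 | 18% v 45% | 25% v 59% |
| 0.4 | 31% v 68% | 46% v 83% |
| 0.5 | 48% v 86% | 68% v 95% |
| 0.6 | 67% v 95% | 86% v 99% |
| 0.8 | 93% v >99% | 99% v >99% |

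At d = 0.5 over 42 to 60 per class, r = 0.3 gives 68-87% v 96-99% and r = 0.7 gives 36-54% v 75-89%. With 30 per class (d = 0.5, r = 0.5) the figures are 33% v 72%. Simulating 1-to-5 items with a ceiling keeps the gap: 42% v 79% at 42 per class and 60% v 93% at 60.

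**The same tests when only k of nine items differ.** With d = 0.5 and r = 0.5, the MANOVA has D2 = 0.5 x (k - 0.1k^2). The mean score has k^2 x 0.25/45 = k^2/180.

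| k | D2, MANOVA | D2, mean | 42 per class | 60 per class |
|---|---|---|---|---|
| 1 | 0.45 | 0.006 | 48% v 6% | 68% v 7% |
| 4 | 1.20 | 0.089 | 94% v 27% | 99% v 37% |
| 8 | 0.80 | 0.356 | 78% v 77% | 94% v 90% |
| 9 | 0.45 | 0.45 | 48% v 86% | 68% v 95% |

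The MANOVA is far ahead for one to four items, about level at eight, and behind only when the shift is close to uniform.

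**Skipped items.** A complete-case MANOVA loses anyone who omits an item. If each item were skipped independently by 2% or 5% of respondents, the loss would be 1 - 0.98^9 = 17% or 1 - 0.95^9 = 37%. The documents report no skipping rate, and skipping concentrated in a few people would cost less.

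**The case against.** A reader might infer that the MANOVA is likely to miss a class preference and should be dropped for a mean score. The documents do not support that, for three reasons.

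- Nothing shows that the nine items measure one thing. The sample items cover satisfaction with the class and also "How likely are you to continue to study and practice the skills you learned in this class". No correlation or factor structure is given. If the classes differ on some items only, the mean score is much the weaker test.
- Even for a uniform 0.5 SD shift, MANOVA power exceeds 50% in four of the six combinations of correlation and class number above. At 0.8 SD it is 82% or more throughout.
- The SAP does not say that the t-tests depend on a significant MANOVA, although calling it an omnibus test suggests so. If they do not, at least one Bonferroni-adjusted item test is significant 74% of the time at 42 per class (d = 0.5, r = 0.5), so 48% may understate the whole procedure.

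A reader might also infer that the plan cannot show which class was preferred. The planned t-tests are signed, so direction is available item by item. What is missing is one overall estimate. Nor is Bonferroni an error: it controls family-wise error validly, and it applies only where post-hoc tests were done.

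The consequence is also limited. Satisfaction belongs with implementation, and the mixed models for cognition and health are untouched. All of this stands, and it is why the MANOVA is kept. It does not argue against Holm, or against reporting a mean score as well.

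**Conclusion.** The point holds as a low-cost improvement, not as a fault that invalidates the analysis. Holm's advantage over Bonferroni follows from its thresholds and needs no assumption about the data. Its size, roughly 0.7 to 0.9 more items flagged out of nine, rests on the assumed 0.5 SD uniform shift, correlation 0.5 and 42 to 60 per class. It does not raise the chance of finding any item.

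The mean score has a real advantage for a near-uniform difference of 0.3 to 0.5 SD, provided that the nine items are indeed the dependent variables. The documents cannot show whether such a difference is the one to expect, so the score is justified as an addition only. Clustering within class rounds is ignored in these calculations and would affect both tests.

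**What to change.** In the SAP's Data Analytic Approach:

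1. Replace Bonferroni with Holm for every post-hoc set. It uses the same unadjusted p-values. The SAP plans adjusted p-values, not adjusted intervals, so nothing it promises is lost.
2. State what the MANOVA's dependent variables are for satisfaction, and keep the item-level MANOVA.
3. Add a mean satisfaction score, computed from the items each respondent answered, as the summary comparison. Report the class difference with its 95% CI.

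No new data are needed. The cost is one additional reported comparison. A mean score dilutes item-specific differences, which the retained item analysis covers. The plan is written in the past tense, so if the satisfaction results have already been seen, the mean score should be labelled as added afterwards.

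### Holm adjustment would serve the post-hoc tests of the one-timepoint measures at least as well as Bonferroni, at the same family-wise error; the gain is modest and this is not an error

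*SAP*

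**What the plan says.** The Data Analytic Approach section of the SAP treats two kinds of outcome in turn.

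The first is data collected once: "we examined measures collected at one timepoint (i.e., implementation, satisfaction"). Where such a measure has several components, the plan describes "using a multivariate ANOVA (MANOVA) as an omnibus test for measures with multiple dependent variables". The next sentence is the one at issue: "If post-hoc analyses were completed, Bonferroni adjusted pvalues were applied". It is followed by "Pairwise comparisons were examined with independent t-tests for continuous variables and Chi-square analyses for binary variables". There are only two classes, so a post-hoc set here is naturally one MBSR versus Brain Health comparison per dependent variable. The number of comparisons is not given. The Protocol (Measures) describes satisfaction as measured by an "anonymous nine-item questionnaire created by the authors", so nine is a plausible set size if each item is a dependent variable.

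The second kind is data collected at several visits, analysed by linear mixed models, with class and "time (preintervention, post-intervention, and six month follow-up) were entered as fixed effects". The SAP says that the main effects and the "class x time interaction (reflecting intervention effects) were examined". It states no visit contrasts and no multiplicity adjustment for these models.

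**The concern.** Bonferroni compares every p-value in a set of m tests with alpha/m. Holm uses that threshold only for the smallest p-value and relaxes it as hypotheses are rejected. Both protect the family-wise error at alpha, and neither needs any assumption about how the tests are correlated. A plan that names Bonferroni therefore accepts somewhat lower power for individual items and receives no extra protection against false positives.

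What is at stake is limited. If the classes differ on several components of satisfaction or implementation, Bonferroni will identify fewer of them. Efficacy conclusions are not affected, because the plan reads the intervention effect from the class by time interaction in the mixed models.

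**Working it through.** **Inputs from the documents**
- Method: Bonferroni (SAP, Data Analytic Approach).
- Set size: not stated. I take m = 9, from the nine satisfaction items (Protocol, Measures), assuming each is tested.
- Number per class: not stated in the text available. Six rounds of 7 to 10 participants (Protocol, Treatment Protocol) give 6 × 7 = 42 to 6 × 10 = 60, before any exclusions for missed classes.

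**Assumptions, for illustration only:** alpha 0.05 two-sided, a standardised difference d = 0.5 on each item that truly differs, correlation 0.5 between items, no dropout.

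The plan gives no power or adjusted threshold, so it has no figure of its own to reproduce.

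**Step 1: thresholds.** Bonferroni compares all nine p-values with 0.05/9 = 0.0056. Holm compares the ordered p-values with 0.05/9 = 0.0056, 0.05/8 = 0.00625, 0.05/7 = 0.0071, and so on up to 0.05/1 = 0.05, stopping at the first failure. Every Holm threshold is at least 0.0056, so whatever Bonferroni rejects, Holm rejects. The first threshold is identical, so the chance of at least one rejection is identical too.

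**Step 2: error control.** Suppose m0 of the m null hypotheses are true. When Holm first reaches a true null, at most m − m0 hypotheses have been rejected, so at least m0 remain and the threshold is at most 0.05/m0. By the union bound, the chance that any true null has a p-value that small is at most m0 × 0.05/m0 = 0.05. No independence is needed, which is the same basis as for Bonferroni.

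**Step 3: size of the gain.** I take simulated average power per true difference, with post-hoc tests counted only after a significant MANOVA:

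| Items that truly differ | 42 per class: Bonferroni → Holm | Gain (points) | 60 per class: Bonferroni → Holm | Gain (points) |
|---|---|---|---|---|
| 1 of 9 | 0.239 → 0.240 | 0.1 | 0.429 → 0.429 | 0.0 |
| 3 of 9 | 0.294 → 0.307 | 1.3 | 0.463 → 0.480 | 1.7 |
| 9 of 9 | 0.247 → 0.310 | 6.3 | 0.423 → 0.518 | 9.5 |

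With correlation 0.6 and all nine differing, the figures are 23% → 28% at 42 per class and 40% → 48% at 60, gains of 5 and 8 points. A fresh simulation agreed with these figures to within about one point.

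**Step 4: if the MANOVA need not be significant.** At 60 per class and correlation 0.5, the power figures become 0.471 → 0.472 with one true difference, 0.463 → 0.481 with three, and 0.469 → 0.579 with nine. The pattern is the same, with a top gain of 11 points.

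**Step 5: what Holm does not recover.** With all nine items differing, requiring a significant MANOVA lowers the chance of any rejection from 0.743 to 0.491 at 42 per class, and from 0.886 to 0.687 at 60. These figures are the same for Bonferroni and Holm.

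**The case against.** The strongest reply is that Bonferroni is valid, simple and pairs directly with simultaneous confidence intervals, and that a few points of per-item power on satisfaction and implementation change no conclusion about efficacy. That stands, and it is why this is only a suggestion. The intervals are no reason to keep Bonferroni for the tests, since Bonferroni intervals can be shown next to Holm-adjusted p-values.

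A second reply is that the larger gains are a best case. This also stands. They need every item to differ by the assumed 0.5. With one true difference Holm adds nothing, and with three it adds 1 to 2 points.

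Two stronger readings are tempting, and the documents support neither.

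- **A formal hierarchical rule.** A reader might infer that post-hoc tests are allowed only after a significant MANOVA, and that Holm restores the power this costs. The SAP calls the MANOVA an omnibus test but does not make later tests depend on its result. If it did, Holm would not restore that loss (step 5).
- **A needless factor of 3 on the visits.** With three visits, a reader might argue that after a significant 2-df time or class by time test, each visit contrast could be tested at 5% unadjusted. But the Bonferroni sentence sits with measures that have no visits, and the plan states no visit-level post-hoc set. The shortcut is valid only for the three pairwise visit contrasts of the same 2-df effect. It does not cover class differences at each visit, or changes within one class. In simulation (correlation 0.6, a true effect at post-intervention only, d = 0.5 to 0.8, 42 or 60 per class), testing the class difference at each visit at 5% after a significant interaction gave a family-wise error of about 7% to 9%. Writing unadjusted 5% tests into a plan whose follow-up contrasts are undefined could replace a valid rule with an invalid one.

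**Conclusion.** The point holds as an efficiency improvement for the post-hoc tests of implementation and satisfaction. That Holm is never worse than Bonferroni, at the same family-wise error, is a mathematical fact and rests on none of the assumed inputs. The size of the benefit does rest on them: for nine items it is nil with one true difference, 1 to 2 points with three, and about 5 to 10 points per test if all nine differ by 0.5, slightly more if no significant MANOVA is required. Set size, alpha, effect size, correlation and number per class are all assumed or derived, so these figures are illustrations, not estimates of what this trial loses. The plan contains no error here, and nothing follows for the mixed-model outcomes.

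**What to change.** Replace the Bonferroni sentence with wording such as: *Where post-hoc tests are carried out, p-values are Holm-adjusted within each set of tests.* It would help to name each set in the same sentence, for example the satisfaction items, since the adjustment depends on the number of tests. Bonferroni simultaneous intervals may still be reported. Do not add a clause allowing unadjusted 5% contrasts between visits.

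The cost is one sentence and one function argument, with no loss of error control. The SAP is written in the past tense. If the results were already known when the change is made, keep the Bonferroni result as the stated analysis and label the Holm result as supplementary.
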